## 8. PHARMACEUTICAL INFORMATION

A list of the adverse events and potential risks associated with the investigational agents administered in this study can be found in [Section 10.1](#).

### 8.1 CTEP IND Agent(s): N/A

### 8.2 Other Investigational Agent

#### 8.2.1 NT-I7 (*rhIL-7-hyFc*), NSC # 805638

**Other Names:** GX-I7 by Genexine, Inc

**Classification:** Cytokine

**M.W.:** 104 KDa

**Mode of Action:** Multifunctional cytokine critical for T-cell development and homeostasis.

**Description:** NT-I7 has a molecular weight of 104 KDa and is composed of 400 amino acids with 155 amino acids for IL-7 and 30 for the IgD hinge, 8 for IgD the CH2 domain, and 207 for the IgG4 region. NT-I7 contains 11 disulfide bonds, 1 O-glycosylation and 3 N-glycosylation sites. NT-I7 protein is produced by inserting the gene expressing rhIL-7-hyFc into the eukaryotic expression vector pAD15 at the Multiple Cloning Site. The CHO cell line DG44 is used to produce NT-I7.

**How Supplied:** NT-I7 is supplied by NeoImmuneTech, Inc. Each single-use 1.0 mL vial contains 25 mg of NT-I7 at a concentration of 25 mg/mL, as a sterile, clear, colorless solution, pH approximately 5. In addition to the active ingredient NT-I7 (rhIL-7-hyFc), each vial contains sucrose, D-sorbitol, tri-sodium citrate dihydrate, citric acid monohydrate, and Polysorbate 80 as a stabilizer and buffer. These ingredients meet the specification criteria of the European pharmacopeia (Ph. EUR).

**Preparation:** The entire preparation process should be carried out in a sterile environment to prevent possible contamination. The dose volume of NT-I7 will be determined based on the assigned dose level and the subject's body weight. For more information, please refer to [Appendix B](#).

The site pharmacy must verify the total dose which is based on the subject's body weight with the site clinical team prior to NT-I7 preparation.

Registered research nurses may prepare NT-I7 syringes for administration. In such cases, site pharmacy will verify the total dose, based on the subject's body weight, with the site clinical team, and will dispense the vial(s) with pharmacy labeling indicating pharmacist-calculated dose volume to be withdrawn into syringe. Prior to administering NT-I7, two research nurses will verify the dose volume calculation and the volume of NT-I7 in the prepared syringe.

The NT-I7 finished drug product should be a colorless, clear solution and should not contain any particulate matter that can be observed visually. There should not be any floating particulates under gross observation. DO NOT SHAKE vials before injection.

**Storage:** Vials that contain NT-I7 must be kept refrigerated at 2~8°C. **NT-I7 vials should never be frozen or shaken.** It is recommended that vials are protected from direct light until the time of use.

If a storage temperature excursion is identified, promptly return NT-I7 to 2~8°C and quarantine the supplies. Provide a detailed report of the excursion to [[contact]](mailto:[contact]) for determination of suitability.

**Stability:** The site pharmacy should prepare the NT-I7 dose syringes in proximity to the time of dose administration. Vials should be removed from the refrigerator 1 to 2 hours before use to achieve room temperature prior to administration. Vial contents should never be frozen or shaken. The room-temperature stability of NT-I7 has been confirmed in a vial for up to 48 hours and in a disposable syringe for up to 24 hours.

**Route and Method of Administration:** The maximum volume that may be administered per intramuscular (IM) injection is 1 mL. Dose volumes greater than 1 mL are to be divided into multiple injections. Inject slowly (over 10-20 seconds) into Deltoid muscle or muscle of the thighs or buttocks, away from joints, nerves or bones. Rotate injection sites with each injection. For information on the injection sites, please refer to [Appendix B](#).

**Patient Care Implications:** Advise study subjects to use effective contraception while receiving study treatment and for at least 3 months (90 days) for both male participants and female participants after the last dose of study treatment.

For patients with a Body Mass Index (BMI)  $>30 \text{ kg/m}^2$ , an adjusted body weight will be used to calculate the final dose to be administered. Please refer to [Appendix B](#) for details on the adjusted body weight calculation.

#### 8.2.2 Agent Ordering and Agent Accountability

NT-I7 will be supplied by NeoImmuneTech Inc. to each participating site. Instructions for ordering the agent can be found in the Study Procedures Manual for the study.

##### 8.2.2.1 Agent Inventory Records

The investigator, or a responsible party designated by the investigator, must maintain a careful record of the receipt, dispensing and final disposition of all agents received from NeoImmuneTech Inc. using the NCI Drug Accountability Record Form.

#### 8.2.3 Investigator Brochure Availability

The current version of the IB for the agent will be distributed to site investigators and research staff by the CITN Central Operating and Statistical Center (COSC). Questions about the most current version of the IB may be directed to the CITN COSC via email.

### 9. STATISTICAL CONSIDERATIONS

#### 9.1 Study Design/Endpoints

##### 9.1.1 Primary Endpoint

#### 9.1.1.1 Adverse Events and Dose Limiting Toxicity

Three participants will be enrolled at dose level 1. If 0 of 3 have a DLT, dosing will escalate to the next highest dose level. If 1 of 3 have a DLT, that dose level will expand to 6 participants. If 1 of 6 participants has a DLT, dosing will escalate to the next highest level. If 0-1 participants have a DLT at dose level 3, an additional 3 participants will be treated at that level.

If 2 participants have a DLT at dose level 1 or dose level -1, dosing will de-escalate to the next lowest level. If 2 participants have a DLT at dose level -2, the study will be stopped.

The RP2D will be no higher than the highest dose at which 0-1 of 6 participants has a DLT, or the level below a dose level with 2 DLTs. Additional RP2D considerations will be based on PD of ALC, CD4+ and CD8+ T cell responses, and the totality of the AE beyond the 28-day window.

DLTs will be defined as any AE that is considered to be at least possibly, probably, or definitely related to the protocol treatment (NT-I7), that occurs within the first 28 days of dose 1 of NT-I7 (i.e., from Week 0 Day 1 through Week 4 Day 7) and that meets at least one of the non-hematologic or hematologic criteria defined in the protocol.

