**Figure 6: 3+3 Phase 1 study design schema.**

All participants enrolled into this study will receive NT-I7 IM injections at the scheduled dose level (Table 8). Participants will be treated at a given dose level every 9 weeks for up to 27 weeks (4 doses) and followed for an additional 12 months. NT-I7 will be held if the ALC is greater than 10,000 cells/ $\mu$ L at the time of administration. There will be no intra-participant dose escalation.

Three participants will be enrolled at dose level 1. If 0 of 3 have a DLT (described in [Section 6.2](#)), dosing will escalate to the next dose level. If 1 of 3 have a DLT, that dose level will expand

to 6 participants. If 1 of 6 participants has a DLT, dosing will escalate to the next highest level. If 0-1 participant has a DLT at dose level 3, an additional 3 participants will be treated at that level.

If two participants have a DLT at dose level 1 or dose level -1, dosing will de-escalate to the next lowest level. Dose levels -1 (360  $\mu\text{g}/\text{kg}$ ) and -2 (240  $\mu\text{g}/\text{kg}$ ) have been defined if there is unexpected toxicity at dose level 1.

The recommended phase 2 dose (RP2D) will be selected according to the following logic, taking into account the MTD determination from the Dose Escalation Phase (Phase I) and the Maximum Effective Dose (MED) level which is defined as the dose level at which maximum effects on peripheral blood T-cell levels and intratumor T-cell levels are observed. The intratumor T-cell levels will dominate if the peripheral blood and intratumor T-cell levels differ. The available data will be assessed by the Protocol PI(s), the Protocol Chair, and the CITN Central Operating and Statistical Center (COSC) to select the RP2D.

- If the MTD is determined AND
  - MTD = MED, then the RP2D = MTD = MED
  - MTD > MED, then the RP2D = MED
- If the MTD is not reached, then the RP2D = MED

Treatment emergent adverse events will be tabulated according to grade and attribution ( $\geq$  possibly attributed to NT-I7 versus  $\leq$  unlikely related to NT-I7).

Response to therapy will be evaluated by clinical exam using AIDS Clinical Trials Group Criteria ACTG criteria at baseline, 9 weeks, 13 weeks, 18 weeks, 27 weeks, and 36 weeks as outlined in the Trial Schema.

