## 9.2 Sample Size/Accrual Rate

Two participants at minimum and a maximum of 6 participants at each dose level will be treated. Up to 2 participants who do not complete at least one year of follow up for reasons other than toxicity or disease progression may be replaced. Up to twenty patients will be enrolled in the study.

This protocol is designed to meet clinical needs of women and members of minority groups. The planned enrollment report (below) is based on US HIV demographics and previous studies.

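### The RP2D ceiling is set by two unequal standards, and one of them lets a dose level with only 3 treated participants become the ceiling

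*Combined protocol and SAP*

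**What the plan says.** Sections 6 and 9.1.1.1 give matching escalation rules. In Section 9.1.1.1:

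- After a clean cohort the trial moves on: "If 0 of 3 have a DLT, dosing will escalate to the next highest dose level".
- Below the top dose, the only trigger for expansion is one DLT: "If 1 of 3 have a DLT, that dose level will expand to 6 participants".
- The top dose alone is expanded after a clean cohort as well: "If 0-1 participants have a DLT at dose level 3, an additional 3 participants will be treated at that level". Section 6 repeats this.
- De-escalation is written for two levels only: "If 2 participants have a DLT at dose level 1 or dose level -1, dosing will de-escalate to the next lowest level". No number to treat at the lower level is given.
- The cap has two limbs. One sets a standard by count: "The RP2D will be no higher than the highest dose at which 0-1 of 6 participants has a DLT". The other, offered as an alternative in the same sentence, sets none: "or the level below a dose level with 2 DLTs".

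Section 9.2 adds that "a maximum of 6 participants at each dose level will be treated", with a minimum of two. Six per level is thus allowed but not required. Section 6 makes the choice of RP2D depend on the MTD and the maximum effective dose, but no sentence says how many participants must have been evaluated at a level before it is called the MTD.

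**The concern.** Estimating the MTD and/or RP2D is part of the primary objective (Sections 1.1.1 and 9.1.1.2), and the sentence on the ceiling is the plan's only DLT-based limit on the RP2D. It applies two standards to one decision. If dose level 3 is reached and tolerated, the ceiling needs 6 participants with at most one DLT. If toxicity appears at level 2 or 3, the level below can become the ceiling on 3. The weaker evidence is accepted in the case where toxicity has been seen inside the dose range. Because the limbs are joined by "or" with no order of precedence, two analysts following the text could also report different ceilings.

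**Working it through.** **Plan's own figure.** Maximum enrolment is 20 (Section 9.2). Three levels × 6 + 2 replacements = 20. The documents do not show this derivation; it is inferred.

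**Paths through the written rule**

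| Level 1 | Level 2 | Level 3 | Ceiling by 0-1 of 6 | Ceiling by level below 2 DLTs |
|---|---|---|---|---|
| 0/3 | 2/3 | not reached | none qualifies | level 1, n = 3 |
| 1/6 | 0/3 | 2/3 | level 1, n = 6 | level 2, n = 3 |

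**What the counts say about the DLT rate** (exact one-sided 95% upper bound; with zero events it is 1 − 0.05^(1/n)):

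- 0/3: 1 − 0.05^(1/3) = 63.2%
- 0/6: 1 − 0.05^(1/6) = 39.3%
- 1/6: Clopper-Pearson, 58.2%

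At a true DLT rate of 40%, 0/3 occurs with probability 0.6³ = 21.6%. Being 0/3 and then having at most 1 DLT in 3 more occurs with probability 0.216 × 0.648 = 14.0%.

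**How often the ceiling rests on 3.** The documents give no DLT rates, so these are assumptions for levels 1/2/3, with rates at levels −1 and −2 set to three-quarters and one-half of the level 1 rate. Cohorts are full, two or more DLTs are read as 2 DLTs, the same 3+3 steps are used after de-escalation, and a level already treated is not expanded. With q = 1 − p:

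- leave a level on 3 participants: q³
- leave it on 6: 3pq² × q³
- pass, g(p) = q³ + 3pq⁵
- pass at level 3, h(p) = q³ × P(at most 1 of 3) + 3pq² × q³

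Worked for .05/.10/.20: g(.05) = .973, g(.10) = .906, h(.20) = .655.

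- Ceiling at level 3: .973 × .906 × .655 = .578
- Ceiling at level 2 on 3: .973 × .729 × (1 − .655) = .245
- Ceiling at level 1 on 3: .857 × (1 − .906) = .080
- Ceiling at level −1 or −2 on 3: .024
- Total on 3: .245 + .080 + .024 = .349

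Exact enumeration for all curves, with the column on the right requiring 6 participants and at most one DLT, and otherwise stepping down:

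| Assumed DLT rates | On 3, all trials | On 3, given ceiling below level 3 | Mean N as written | Mean N if 6 required |
|---|---|---|---|---|
| .05/.15/.40 | 64% | 79% | 11.28 | 13.29 |
| .10/.25/.45 | 69% | 76% | 10.52 | 12.77 |
| .15/.40/.60 | 74% | 75% | 9.28 | 11.85 |
| .05/.10/.20 | 35% | 83% | 12.14 | 13.21 |
| .03/.05/.10 | 13% | 89% | 12.36 | 12.75 |

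The rates assumed at levels −1 and −2 matter little: setting them to zero, or equal to level 1, moves the 74% between 73% and 78% and the others by less than 2 points.

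**Effect on the choice.** With .15/.40/.60, the probability that level 2 (true rate 40%) is the ceiling falls from 24.1% to 18.2% if 6 are required.

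**The case against.** - **It is a cap, not a declared dose.** This stands. The sentence says the RP2D may be no higher, does not mention the MTD, and allows pharmacodynamics and later adverse events to lower the choice. A reader might infer that the plan declares an MTD on 3 participants. The documents do not say so; they leave the MTD without an operational definition. But a level seen in 3 participants can still become the RP2D within this cap.
- **The sentence may mean that both limits apply.** That reading is possible, and on it a level passed only at 0/3 never meets the 0-1 of 6 limb. In the 0/3 then 2/3 path no level would then qualify at all. This supports reconciling the limbs; it does not show that the text is adequate.
- **Figure 6 and the label of a traditional 3+3 may supply the missing step.** Figure 6 was not available for review and could show one. A reader might infer that the written sentence would override it; nothing supports that. If the figure does show expansion to 6, the text should say so too.
- **Toxicity may be low.** In GX-I7-CA-003 (Section 10.1.2.2) the one DLT described was at 1700 µg/kg, and 1200 µg/kg was taken as MTD and RP2D; 10 subjects given as 83.3% implies 12 treated at that dose. That was every 3 weeks in solid tumors, so it is only indicative. If rates are low, the 13% row is nearer than the 74% row.
- **An expansion cohort is foreseen (Section 9.4.1).** It is deferred to an amendment, described for efficacy, and comes after the RP2D is chosen.

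**Conclusion.** The point holds as an inconsistency of standard within one decision rule: 0-1 of 6 on one side, no minimum on the other, with no order between them. Following the text can leave the ceiling on 3 participants. Under the assumed curves this happens in 35-74% of all trials in four scenarios and about 13% in a low-toxicity one, and never when dose level 3 passes. The 75-89% column is conditional on the ceiling falling below level 3. A reader might take it as the chance that this trial ends there; it is not, and the documents give no DLT rates from which that chance could be had. Nor do the two limbs contradict each other outright, since they are joined by "or". The gain in accuracy from requiring 6 is real but modest. This is a change that should be made; it does not invalidate the design. Which dose or clinical rule is right is not judged here.

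**What to change.** Replace the two limbs by one evidence standard for the RP2D ceiling, and state that it is also the standard for the MTD on which Section 6 relies. The plan's own standard, 0-1 DLTs in 6 DLT-evaluable participants as Section 6.2.1 defines evaluability, would then apply at whichever level is named. State what follows if that level does not meet it. Use identical wording in Sections 6 and 9.1.1.1, and check it against Figure 6.

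Cost if 6 are required: about 1.1-2.6 more participants on average in the four curves (0.4 in the low-toxicity one), within the maximum of 6 per level. More than 20 evaluable participants would be needed in at most about 0.6% of trials in those curves, and in 1.3% under a steeper assumed curve (.10/.15/.25/.40/.55 for levels −2 to 3). The theoretical maximum is 5 levels × 6 = 30, so the plan should say what happens at the cap. Replacement of unevaluable participants has no stated limit: if 10% are assumed unevaluable, enrolment passes 20 in about 1.8-2.9% of trials in the four curves, against 0.3-0.8% as written.

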#### 9.1.1.2 Primary Objective

To determine the safety and adverse event profile of NT-I7 dosed at 480  $\mu\text{g}/\text{kg}$ , 960  $\mu\text{g}/\text{kg}$ , and 1200  $\mu\text{g}/\text{kg}$  in patients with KS with or without infection with HIV, including estimation of the maximum tolerated dose (MTD) and/or the recommended Phase 2 dose (RP2D).

#### 9.1.1.3 Primary Hypothesis

NT-I7 dosed at 480  $\mu\text{g}/\text{kg}$ , 960  $\mu\text{g}/\text{kg}$  and 1200  $\mu\text{g}/\text{kg}$  is safe and tolerable in patients with KS with or without infection with HIV.

## 9.2 Sample Size/Accrual Rate

Two participants at minimum and a maximum of 6 participants at each dose level will be treated. Up to 2 participants who do not complete at least one year of follow up for reasons other than toxicity or disease progression may be replaced. Up to twenty patients will be enrolled in the study.

This protocol is designed to meet clinical needs of women and members of minority groups. The planned enrollment report (below) is based on US HIV demographics and previous studies.

### PLANNED ENROLLMENT REPORT

Racial Categories	Ethnic Categories				Total
	Not Hispanic or Latino		Hispanic or Latino		
	Female	Male	Female	Male	
American Indian/ Alaska Native		1			1
Asian		1			1
Native Hawaiian or Other Pacific Islander		1			1
Black or African American	1	4	1	3	9
White	0	3	0	3	6
More Than One Race	0	1	0	1	2
Total	1	11	1	7	20

PHS 398 / PHS 2590 (Rev. 08/12 Approved Through 8/31/2015)

OMB No. 0925-0001/0002

### 9.3 Stratification Factors

Patients will not be stratified.

### 9.4 Analysis of Secondary Endpoints

#### 9.4.1 Objective Response Rate (ORR) to NT-I7 in HIV-positive and HIV-negative adults with KS

To preliminarily evaluate the objective response rate of KS to NT-I7 across all dose levels, KS response will be assessed according to modified ACTG criteria. For primary analysis the best response obtained within 12 months of the first dose of NT-I7 will be used, in all participants administered across study doses. Subset analyses for participants by dose level, HIV status, baseline CD4 greater than or less than 200 cells/uL, and history of prior chemotherapy for any subset in which there are at least 6 participants. A more precise estimate of efficacy will occur in a RP2D expansion cohort where dosing will be uniform. An expansion cohort will be included in an amendment.

#### 9.4.2 Duration of Response, Progression-free Survival, and Overall Survival of HIV-positive and HIV-negative adults with KS Treated with NT-I7

Statistical methods for censored time-to-event data will be used to estimate overall survival, progression-free survival and duration of response along with 95% CI bands. Kaplan Meier survival estimates will be constructed for each of these survival endpoints with 95% CIs, for up to 1 year following initiation of treatment in all participants. Overall survival will be defined as the time from administration of the first dose of NT-I7 until death or censoring, progression free survival will be defined as the time from administration of the first dose of NT-I7 until disease progression or death or censoring, and duration of response will be measured in subjects who obtain a partial response or better and defined as time from the best response within the first 36 weeks of therapy until disease progression or censoring. Subsequently, Cox proportional hazards regression will be used to estimate hazard ratios with 95% CIs for HIV-positive versus HIV-negative participants, adjusted for disease stage.

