### 12.1.2 Kaposi sarcoma Response Criteria

#### 12.1.2.1 Complete Response

The absence of any detectable residual disease, including tumor associated edema, persisting for at least 4 weeks.

- For subjects with pigmented macular skin lesions persisting after apparent complete response, a biopsy of at least one representative lesion is required to document the absence of malignant cells. If a lesion has not been biopsied, the patient may be classified as having a clinical CR.
- For subjects with visceral disease, the diagnostic radiologic or endoscopic study should be repeated if not medically contraindicated and found to be negative for evidence of disease. If such procedures are medically contraindicated but the patient has no clinical evidence of visceral disease, the patient may be classified as having a clinical CR.

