#### 12.1.2.3 Partial Response

No progressive disease (see below and noting, that single lesions which split up into 2 or more smaller lesions during the course of treatment will still be counted as one); no new lesions occurring in previously uninvolved areas of the body; no new visceral sites of involvement or the appearance or worsening of tumor-associated edema or effusions *and*:

- A 50% or greater decrease in the number and/or size of previously existing lesions **lasting for at least 4 weeks or**
- Complete flattening of at least 50% of all previously raised lesions (i.e., 50% of all previously nodular or plaque-like lesions become macular) **lasting for at least 4 weeks or**
- A 50% decrease in radiologically measurable visceral lesions sustained without evidence of re-growth **for at least 4 weeks or**
- A 50% decrease in radiologically measurable visceral lesions sustained without evidence of re-growth **for at least 4 weeks or**
- Subjects who otherwise meet the criteria for a CR but still have residual tumor-associated edema or effusions will be classified as having a PR.

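### Duration of response in 9.4.2 runs from best rather than first response, so a participant who improves from PR to CR is credited with a shorter duration; death is not named as an event, and the response window is shorter than the one for ORR.

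*Combined protocol and SAP*

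**What the plan says.** DOR is part of secondary objective 1.2.3. Its only operational definition is in section 9.4.2:

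- **Population:** "duration of response will be measured in subjects who obtain a partial response or better".
- **Start and end:** "defined as time from the best response within the first 36 weeks of therapy until disease progression or censoring".
- **Comparator in the same sentence:** progression-free survival (PFS) runs from first dose "until disease progression or death or censoring".
- **Kaplan-Meier horizon** for overall survival, PFS and DOR alike: "for up to 1 year following initiation of treatment in all participants".

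For ORR, section 9.4.1 says "the best response obtained within 12 months of the first dose of NT-I7 will be used". Section 6 schedules response by "ACTG criteria at baseline, 9 weeks, 13 weeks, 18 weeks, 27 weeks, and 36 weeks". After that, section 6.6 and Study Calendar footnote d provide 12-weekly assessments until a year after the last dose.

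Both response categories need persistence. CR is "The absence of any detectable residual disease, including tumor associated edema, persisting for at least 4 weeks" (12.1.2.1), and the PR criteria on lesion number, size and flattening must be met "lasting for at least 4 weeks" (12.1.2.3). Neither 9.4.1 nor 9.4.2 says whether that confirmation must fall inside its response window.

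The reference for progressive disease (PD) differs by place. Section 12.1.2.4 compares with baseline, for what it calls the primary outcome analysis. Appendix D (2.4, Progressive Disease) compares with best response once a PR or CR has been confirmed.

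**The concern.** A duration endpoint should not penalise a better outcome. With the clock at best response, the time already spent in PR is dropped whenever the participant goes on to CR. The deeper response is then reported as the less durable one.

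The omission of death matters because PFS names it in the same sentence. A programmer would most naturally censor a responder who dies without PD, which treats that responder as if the response could have continued. The unequal windows mean that the responders counted in ORR and those with a DOR need not be the same people.

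With few responders, one redated start or one recoded death can visibly move the curve. If the wording stays, these choices may be made after the data have been seen.

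**Working it through.** The plan gives no target, event count or precision for DOR, so there is no planned figure to reproduce. The check compares the definitions and applies date arithmetic to the scheduled visits.

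**1. Start date.** Inputs are the on-treatment visits at weeks 9, 13, 18, 27 and 36 (section 6). Loss = week of CR minus week of first PR.

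| First PR | CR at 13 | CR at 18 | CR at 27 | CR at 36 |
|---|---|---|---|---|
| 9 | 4 | 9 | 18 | 27 |
| 13 | – | 5 | 14 | 23 |
| 18 | – | – | 9 | 18 |
| 27 | – | – | – | 9 |

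A CR first seen at week 13, 18 or 27 can be confirmed at the next visit, by week 36. The loss is then 4 to 18 weeks. The last column needs a CR first seen at week 36 and confirmed afterwards. If that is allowed, the loss reaches 27 weeks.

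Worked case: PR at weeks 9 and 13, CR at weeks 18 and 27, PD at week 36.
- DOR under 9.4.2: 36 − 18 = 18 weeks.
- Same first response and PD date, PR throughout: 36 − 9 = 27 weeks.
- The improver is 9 weeks (9/27 = 33%) shorter.

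**2. Death.** The PFS wording lists progression, death and censoring. The DOR wording lists progression and censoring only. No other section supplies a death rule for DOR.

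For scale only, take the 5-year survival in section 2.1.2 (54% HIV-associated, 87% uninfected) and assume a constant hazard, h = −ln(S)/260 per week. A best response at week 36 or week 9 leaves 16 or 43 weeks to week 52.
- HIV-associated: 1 − exp(−16h) = 3.7%; 1 − exp(−43h) = 9.7%.
- Uninfected: 0.9% and 2.3%.
- With an assumed 5 responders, the expected number of deaths is 0.19 to 0.48 if all are HIV-associated and 0.04 to 0.11 if all are uninfected.
- If all 20 participants responded and all were HIV-associated, the upper figure is 20 × 9.7% = 1.94.

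These are expected all-cause counts, not maxima. They include deaths after PD, which do not affect DOR.

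**3. Response windows.** Twelve months is 365.25/7 = 52.2 weeks, so the gap after week 36 is about 16 weeks. Counting 12-weekly follow-up from the last dose (weeks 0, 9, 18 or 27), the visits between weeks 36 and 52, with the next visit in brackets, are:
- 1 dose: 48 (none)
- 2 doses: 45 (57)
- 3 doses: 42 (54)
- 4 doses: 39 (51) and 51 (63)

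If confirmation must fall by week 52, one of these five visit slots can give a late confirmed first response (week 39, confirmed at 51). If it may fall later, four can. Counting from week 36 instead leaves one slot, week 48, confirmed at week 60. These are visit slots, not probabilities.

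**4. PD reference.** Appendix D, 2.1 has a participant with lesion area 5000 mm² at entry and 2000 mm² at best response. The 25% threshold is 5000 × 1.25 = 6250 mm² against baseline and 2000 × 1.25 = 2500 mm² against best response. The choice can change the end date for any responder.

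**The case against.** The strongest reply is proportionality. Section 9.4.1 calls the efficacy evaluation preliminary and leaves a more precise estimate to an expansion cohort to be added by amendment. DOR will rest on a handful of responders, and the RP2D does not depend on it. That stands, and it lowers the priority. It does not make the definition sound.

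It can also be said that 36 weeks is a natural choice, being four 9-week cycles and the last on-treatment assessment. A DOR limited to on-treatment responses would be defensible if the plan said so and explained why ORR differs.

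The worked case holds the PD date equal, whereas Appendix D tests PD differently after CR (any KS) and after PR (at least a 25% increase). That is fair, and real pairs will not match so neatly. Holding the end date fixed simply isolates the effect of the start date.

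Four stronger readings are tempting, and the documents do not support them:
- **The 1-year Kaplan-Meier horizon is an error.** It matches the ORR window and the one-year follow-up in the replacement rule of 9.2. Kaplan-Meier handles administrative censoring; the cost is precision, not bias. Nothing in 9.4.2 bars describing later data.
- **Deaths are censored by rule.** That is the natural reading, but the text does not say it.
- **Every deepening of a PR shortens DOR.** Appendix D, 2.1 lets best response move within PR, and its example would give 24 − 18 = 6 weeks against 24 − 9 = 15. But Appendix D uses that value as the reference for PD, 9.4.2 does not adopt the meaning, and weeks 15 and 24 of the example are not visits in this trial.
- **A 27-week loss is typical.** It needs a CR first seen at week 36 and confirmed later.

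**Conclusion.** The point holds for the definition of DOR. The start at best response is a stated rule with a perverse result: PR-to-CR improvers lose 4 to 18 weeks on the scheduled visits, or up to 27 if late confirmation of CR is allowed. How many participants this affects cannot be estimated from the documents.

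The missing death event is an ambiguity with few expected cases, on the assumption that epidemiological survival at constant hazard applies to responders in this trial. The window mismatch is real but of small reach.

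A reader might infer that DOR is biased in a known direction. The documents do not support that: starting at best response shortens DOR for improvers, whereas censoring deaths would lengthen it. The primary safety objective and the RP2D are untouched. Priority is low to moderate.

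**What to change.** Amend section 9.4.2, with a matching line in 9.4.1:

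1. Define DOR as the time from the first assessment showing a PR or better that is later confirmed, to the first PD or death from any cause.
2. Apply it to every participant counted as a responder for ORR.
3. State whether the 4-week confirmation must fall within the 12-month ORR window.
4. State which PD reference applies to DOR, and reconcile section 12.1.2.4 with Appendix D, 2.4 accordingly.

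Optionally, report DOR over all follow-up scheduled under 6.6 beside the 1-year estimate. Nominal follow-up past week 52 is 0, 9, 18 and 27 weeks after one, two, three and four doses, so the later part of the curve would rest on fewer participants.

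The cost is wording only, with no new visits or data. DOR may look slightly less favourable once deaths count as events.
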